5.11.1.2 Serious Adverse Events

The number and percentage of subjects experiencing at least 1 treatment-emergent SAE will be summarized by MedDRA primary SOC, HLT, and PT.

In addition, a by-subject listing of the SAEs will be presented (the subject listing will contain all SAEs regardless of treatment-emergent status).

5.11.1.3 Deaths

A by-subject listing of the deaths will be presented. All deaths occurring on-study and during follow-up will be displayed (regardless of treatment-emergent status).

5.11.1.4 Adverse Events Resulting in Discontinuation of Study Drug

A by-subject listing of AEs resulting in discontinuation of study drug will be presented.

5.11.2 Laboratory Data

For the purposes of summarization in both the tables and listings, all laboratory values will be converted to standardized units. If a lab value is reported using a nonnumeric qualifier

(e.g., less than (<) a certain value, or greater than (>) a certain value), the given numeric value will be used in the summary statistics, ignoring the nonnumeric qualifier.

If a subject has repeated laboratory values for a given time point, the value from the last evaluation will be used.

The parameters to be analyzed are as follows:

- Hematology: hemoglobin, hematocrit, platelet count, neutrophils (absolute neutrophil count [ANC]), lymphocytes, monocytes, eosinophils, basophils, and leukocyte counts
- Clinical chemistries: blood urea nitrogen (BUN), creatinine, bilirubin (total), urate, lactate dehydrogenase (LDH), phosphate, gamma-glutamyl-transferase (GGT), albumin, alkaline phosphatase (ALP), aspartate aminotransferase (AST), alanine aminotransferase (ALT), glucose, sodium, potassium, calcium, chloride, CO₂, magnesium, amylase, and lipase
- Urinalysis: turbidity and color, pH, specific gravity, protein, ketones, bilirubin, blood, nitrite, urobilinogen, glucose, leukocytes
- Lipid panel: total cholesterol, high-density lipoprotein (HDL), low-density lipoprotein (LDL), triglycerides
- Thyroid panel: thyroid-stimulating hormone (TSH), triiodothyronine (T3), and thyroxine (T4)
- Immune reconstitution assessments: lymphocyte counts, phenotypic T, B, and natural killer (NK) cell subsets (CD4⁺ T cell counts, CD8⁺ T cell counts, CD8/CD4 ratio, CD19⁺ B cell counts), and NK cells (CD3⁻ CD56 CD16⁺ vsCD3⁻ CD56 CD16⁻)
- Other: hemoglobin A1C

The actual values in clinical laboratory parameters (hematology and serum chemistry, including lipid panel and thyroid panel) will be summarized at baseline and over time by treatment group; summary statistics for change from baseline in laboratory parameters will also be presented.

In addition, hematology and serum chemistry parameters will be summarized in shift tables comparing the baseline visit to the worst post baseline value (National Cancer Institute [NCI] Common Terminology Criteria for Adverse Events [CTCAE] grade, version 4.03, effective 14 June 2010⁽³⁾) for the following parameters.

- Hematology: hemoglobin, , platelet count, neutrophils (absolute neutrophil count [ANC]), lymphocyte counts, and leukocyte counts
- Clinical chemistries: bilirubin (total), alkaline phosphatase (ALP), aspartate aminotransferase (AST), alanine aminotransferase (ALT), amylase, and lipase

Urinalysis results will be presented in a listing.

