- d A serum beta-human chorionic gonadotropin (B-hCG) pregnancy test will be performed during screening only for patients of childbearing potential. A urine pregnancy test will be performed before dosing on Day 1 of all cycles. The results of any pregnancy test must be negative before dosing on Day 1 of all cycles. Additional pregnancy testing may be performed during the study at the discretion of the investigator, upon request of the Independent Ethics Committee (IEC)/Institutional Review Board (IRB), or if required by local regulations.
- e If available and consistent with local regulations, tumor tissue collected at the time of original diagnosis (unstained slides or a paraffin-embedded block) will be obtained during screening after the patient has signed the informed consent form. The sample may be used in the evaluation of a diagnostic test to determine CD30 expression.

CCI

- f Perform vital signs measurement at screening, prior to dosing on Day 1 of each cycle, and at EOT. On Cycle 1, Day 1 only, also perform vital signs measurements at 1 hour (± 10 minutes) postdose for patients receiving brentuximab vedotin. Blood pressure should be determined with the patient in a seated position after the patient has been sitting quietly for 5 minutes.
- g The Cycle 1, Day 1 physical examination is not required if the complete physical examination performed at screening was conducted within 4 days before randomization. A limited physical exam may be administered at the treating physician's discretion.
- h A blood sample for hematology and serum chemistry will be obtained at screening, before dosing on Day 1 of all cycles, and at EOT. For screening, labs must be performed within 4 days of randomization, and do not need to be repeated before dosing.
 Hematology panel includes complete blood count (CBC) with differential consisting of the following: hemoglobin, hematocrit, platelet count, leukocytes with differential, and neutrophils (absolute neutrophil count [ANC]). Machine counts are acceptable.
 Serum chemistry panel includes: sodium, potassium, carbon dioxide, chloride, blood urea nitrogen (BUN), creatinine, total bilirubin, alkaline phosphatase (ALP), aspartate transaminase (AST), alanine transaminase (ALT), lactate dehydrogenase (LDH), albumin, glucose, urate (uric acid), calcium, phosphate, magnesium, GGT, amylase, and lipase.
 Hemoglobin A1C will be obtained at screening and on Day 1 of Cycles 1, 4, 7, 10, and 16.

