6.4.1 Criteria for Beginning or Delaying a Subsequent Treatment Cycle

Treatment with brentuximab vedotin or reference therapy will use a cycle length of 21 days. For a new cycle of treatment to begin, the patient must meet the following criteria:

- ANC must be $\geq 1,000/\text{mm}^3$
- All other study drug-related toxicity must have resolved per the guidelines provided in [Table 6-3](#) and [Table 6-4](#).

If the patient fails to meet the criteria for retreatment cited previously, initiation of the next cycle of treatment should be delayed up to 1 week. At the end of that time, the patient should be re-evaluated to determine whether the criteria for retreatment have been met. The start of the next cycle may be delayed for up to 3 weeks if additional time is required for the patient to recover from study treatment-associated toxicity experienced during the current cycle. Delays of greater than 3 weeks are prohibited without approval of the sponsor.

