8.1.9 Safety Analysis

Safety will be evaluated by the incidence of AEs, severity and type of AEs, and by changes from baseline in the patient's vital signs, ECOG performance status, and clinical laboratory results using the safety population. Exposure to study drug and reasons for discontinuation will be tabulated.

Treatment-emergent AEs that occur after administration of the first dose of study drug and through 30 days after the last dose of study drug will be tabulated. Adverse events will be tabulated according to the Medical Dictionary for Regulatory Activities (MedDRA) and will include the following categories:

- TEAEs
- Study drug-related TEAEs
- Grade 3 or higher TEAEs

Brentuximab vedotin (SGN-35)

Clinical Study Protocol C25001 Amendment 5, EudraCT: 2010-024215-14

- Grade 3 or higher study drug-related TEAEs
- The most commonly reported treatment-emergent AEs (ie, those events reported by $\geq 10\%$ of all patients)
- SAEs

A listing of treatment-emergent AEs resulting in study drug discontinuation will be provided.

Descriptive statistics for both the actual values and change from the baseline assessment values of the clinical laboratory parameters (hematology and chemistry) will be presented for all scheduled measurements over time. Mean laboratory values over time will be plotted for key laboratory parameters. Shift tables for laboratory parameters will be generated based on changes in NCI CTCAE grade from the baseline assessment to the worst postbaseline value.

Descriptive statistics for the actual values (and/or the changes from the baseline assessment) of vital signs over time will be tabulated by scheduled time point.

Eastern Cooperative Oncology Group performance status and change from baseline will be summarized. Shifts from baseline to the worst postbaseline score will be tabulated by treatment group. Patients who have ECOG performance scores that worsen postbaseline compared to baseline will be listed with other pertinent patient information.

Investigators' assessments of ECG monitoring (normal, abnormal and clinically significant, or abnormal and not clinically significant), including unscheduled or retested measurements, will be presented in a listing.

Additional safety analyses may be performed to most clearly enumerate rates of toxicities and further define the safety profile of study drug.

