5.4.3 Windowing of Visits

All data will be categorized based on the scheduled visit at which they were collected. These visit designators are predefined values that appear as part of the visit tab in the electronic case report form (eCRF).

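### SAP 5.11.2 does not confine its last-value rule for repeated laboratory results to by-visit summaries, so the rule can displace the worst value that the shift tables are meant to show

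*SAP*

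**What the plan says.** SAP 5.11.2 places this rule ahead of all the laboratory analyses: "If a subject has repeated laboratory values for a given time point, the value from the last evaluation will be used". It names no analysis to which the rule is confined and none that is exempt.

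Later in the section, hematology and chemistry parameters are to be "summarized in shift tables comparing the baseline visit to the worst post baseline value", by CTCAE grade. The parameters include neutrophils, platelets, bilirubin, liver enzymes, amylase and lipase. Protocol 8.1.9 asks for the same tables, "based on changes in NCI CTCAE grade from the baseline assessment to the worst postbaseline value", and mentions no last-value selection. SAP 6 declares no change from the protocol.

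Three other provisions decide when the two rules meet:

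- **Schedule** (Protocol Schedule of Events, footnote h): "A blood sample for hematology and serum chemistry will be obtained at screening, before dosing on Day 1 of all cycles, and at EOT".
- **Delay** (Protocol 6.4.1): a cycle may begin only if the neutrophil count is at least 1,000/mm³ and other drug-related toxicity has resolved. Otherwise it is delayed by up to a week, and "At the end of that time, the patient should be re-evaluated to determine whether the criteria for retreatment have been met".
- **Filing** (SAP 5.4.3): "All data will be categorized based on the scheduled visit at which they were collected". The labels are predefined in the eCRF. The SAP gives no date windows and no rule for unscheduled or repeat laboratory draws.

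**The concern.** Keeping the last of several values at a visit is an ordinary convention for a table of means by visit. It does not suit a worst-value table, because in this trial the protocol itself produces the repeats. No mid-cycle draw is scheduled, so the pre-dose Day 1 sample is often the only scheduled chance to record a toxic value. When that sample is bad enough to delay treatment, the cycle goes ahead only after recovery. The later of two pre-dose values is then normally the better one, so any loss runs in one direction.

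Laboratory values are part of a listed secondary endpoint (Protocol 3.2). The shift tables are the laboratory-based view of toxicity, and they do not depend on an investigator choosing to record an event. Amylase and lipase were added to the panel in Amendment 5 because of pancreatitis risk. A programmer could follow SAP 5.11.2 to the letter and produce shift tables that leave out some of the values that changed treatment.

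**Working it through.** The plan gives no figure to reproduce here. The check applies the two SAP sentences in each order and then asks how large the effect could be.

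**1. Order of operations.** Take a made-up neutrophil series (per mm³): C2D1 2500, C3D1 2100, C4D1 800, repeated at 1600, C5D1 1900. The value 800 fails the 1,000/mm³ criterion in Protocol 6.4.1, and 1600 meets it.

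| Handling | Value entering the shift table |
|---|---|
| Worst over all draws | min(2500, 2100, 800, 1600, 1900) = 800 |
| Last per visit, then worst; both draws labelled C4D1 | min(2500, 2100, 1600, 1900) = 1600 |
| One of the two draws labelled unscheduled, and unscheduled draws admitted | 800 |

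The result turns on the visit label and the order of selection. The SAP fixes neither for this case.

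**2. Conditions for a loss.** All three must hold for a patient:

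- the failed and repeat draws carry the same visit label;
- the last-value rule is applied before the worst value is chosen;
- no other retained post-baseline draw has an equal or worse grade.

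A patient who never recovers keeps the bad value, because it is the last one. Grade 3 or 4 lymphopenia need not interrupt brentuximab vedotin (Table 6-3, footnote b), so it would not usually lead to such a repeat.

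**3. Scale, for neutrophils only.** Inputs:

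- about 62 patients per arm (SAP 5.1);
- 11% with a new or worsening shift to Grade 3 or higher neutrophils in earlier brentuximab vedotin studies (Protocol 1.3);
- f, the share of those patients who meet all three conditions. The documents give no value for f, so the whole range from 0 to 1 is shown as an assumption.

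Expected patients with such a shift: 62 × 0.11 = 6.8. Patients lost from the table: 6.8 × f. Rate shown in the table: 11% × (1 − f).

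| f (assumed) | Patients lost | Rate shown |
|---|---|---|
| 0 | 0 | 11% |
| 0.25 | 1.7 | 8.25% |
| 0.50 | 3.4 | 5.5% |
| 0.75 | 5.1 | 2.75% |
| 1 | 6.8 | 0% |

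**The case against.** The best defence is that the two sentences can be reconciled. The repeat rule speaks of a given time point, which suits the summaries over time. The shift table is not a time-point summary and has its own selection rule. SAP 5.4.1 also says that all available safety data go into listings and tabulations. On that reading nothing is lost. The reading is reasonable, but the SAP does not state it. A specific rule placed before every laboratory analysis is likely to be programmed ahead of a general statement elsewhere.

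Second, nothing says that a re-test a week later carries the failed draw's label. It falls outside the ±2-day allowance in the Schedule of Events and might be coded unscheduled. It might also be a local result, and the SAP does not say whether local values enter these tables. This stands, and it is why the loss is conditional.

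Third, Protocol 10.1.2 lets a laboratory value that delays treatment be recorded as an adverse event, so it can reach the overall and Grade 3 or higher event tables. This also stands as partial cover. It depends on investigator recording in an open-label trial, and the shift table should serve as a check on that recording.

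A reader might infer three stronger things that the documents do not support:

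- **That the rule also strips values from the listings.** The phrase "For the purposes of summarization in both the tables and listings" introduces the conversion to standard units. The repeat rule is a separate statement that does not mention listings, and SAP 5.4.1 points the other way.
- **That abnormal values are certain to vanish.** All three conditions above are needed, and the true number could be zero.
- **That the comparison between arms is biased in a known direction.** Neither document gives rates of toxicity-driven delay by arm.

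**Conclusion.** The point holds as a conflict between two stated rules, with a foreseeable one-directional effect if they are applied in the wrong order. It does not show that data will be lost. For Grade 3 or higher neutrophil shifts, the possible loss is 0 to about 7 of 62 brentuximab vedotin patients. That range rests on the 11% background rate and an unknown share f. The same mechanism could affect the other shift-table parameters where an abnormal value led to a delay and a repeat test, but the documents do not allow a count.

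The effect is confined to descriptive laboratory shift tables. No hypothesis test, alpha, sample size or efficacy result is touched. The correction is still worth making before the tables are programmed, because these tables are meant to show the worst toxicity and the ambiguity is easily removed.

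**What to change.** In SAP 5.11.2:

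- limit the last-evaluation rule to the by-visit descriptive summaries (actual values and change from baseline);
- state that the shift tables take the worst CTCAE grade over all post-baseline values, including repeat and unscheduled draws.

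It would also help to say whether local laboratory results, which Protocol 7.4.15 allows for treatment decisions, count towards the worst grade. No change is needed for listings, since SAP 5.4.1 already implies that they show every value.

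The cost is one or two sentences and a small programming change, with no new data collection.

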The clinical laboratory parameters for which the most patients had new or worsening shifts to \geq Grade 3 were low neutrophils (11%), lymphocytes (11%), platelets (6%), leukocytes (5%), and high glucose (6%). Only 1 patient in the phase 2 studies had Grade 3 ALT and aspartate aminotransferase (AST).

In the phase 2 studies, 31% of patients had a serious adverse event (SAE), 28% had an SAE of Grade 3 or higher, and 15% had an SAE that was determined by the investigator to be related to brentuximab vedotin. The most common SAEs, reported in \geq 2% of patients, were abdominal pain, disease progression (recurrent sALCL), pulmonary embolism, and septic shock. A higher proportion of sALCL patients experienced SAEs, including deaths within 30 days of last dose, relative to HL patients, likely due to the older age and more aggressive nature of the malignancy in this patient population.

Brentuximab vedotin (SGN-35)

Clinical Study Protocol C25001 Amendment 5, EudraCT: 2010-024215-14

A total of 9 deaths were reported within the safety evaluation period (within 30 days of the last dose of brentuximab vedotin) in 357 patients across the 6 phase 1 and phase 2 studies for which data are available. Two patient deaths (0.6%) were considered related to study treatment. One patient in study SG035-0001 who received 3.6 mg/kg in phase 1 died due to febrile neutropenia and presumed septic shock. A second treatment-related death in study SG035-008A was attributed to pancytopenia, cytomegalovirus (CMV) infection, and intracranial hemorrhage. The remaining on-study deaths were primarily related to disease progression in sALCL patients.

Brentuximab vedotin has been shown to induce durable remissions in patients with HL both pre- and post-ASCT, and in patients with relapsed or refractory sALCL. Progression-free survival results comparing PFS with brentuximab vedotin to PFS from prior systemic therapy indicate that PFS is significantly prolonged with brentuximab vedotin for both HL and sALCL. A substantial number of HL and sALCL patients with B symptoms at baseline saw these symptoms resolve during treatment with brentuximab vedotin. In addition, the large majority of sALCL patients presenting with cutaneous lesions at baseline experienced resolution of these symptoms after receiving brentuximab vedotin.

Further details on clinical studies with brentuximab vedotin are provided in the brentuximab vedotin IB.

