Hypertriglyceridemia of all grades has been recorded in 79% of patients who took bexarotene in a study in early-stage CTCL; hypercholesterolemia occurred in 48% of patients; and hypothyroidism in 40%. Similarly, in a study in advanced-stage CTCL, the incidence of hyperlipidemia of all grades (primarily hypertriglyceridemia) with bexarotene was 82%, hypercholesterolemia was 30%, and hypothyroidism was 29%. Before initiating bexarotene therapy, a patient history should be taken to identify those with familial hypertriglyceridemia, uncorrected hypothyroidism, an individual or family history of myocardial infarction or cardiovascular events, or a history of diabetes. A minority of patients with familial hypertriglyceridemia cannot tolerate bexarotene and should be considered for alternative therapy. A substantial proportion of patients will have pathology related to cardiovascular atherosclerosis or a history of cardiovascular disease and have hypertriglyceridemia that will need to be treated before bexarotene therapy. In addition, those with coronary heart disease are likely to have active atherosclerotic plaques that should be stabilized with low-dose statin therapy (eg, 10 mg daily) 3 days before beginning bexarotene. Diabetes can also contribute to the development of coronary heart disease and should be controlled. These groups of at-risk patients are identified by elevated plasma lipid levels and should be monitored particularly closely during treatment, with measurement of fasting lipid levels at weekly intervals for as long as necessary until it becomes apparent that these are stabilized reliably at the levels recommended.

Prior to dosing with bexarotene, attempts should be made to obtain triglyceride levels that meet the normalized lipid levels per the United States Prescribing Information (USPI)

Brentuximab vedotin (SGN-35)**Clinical Study Protocol C25001 Amendment 5, EudraCT: 2010-024215-14**

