5.11.1 Adverse Events

5.11.1.1 Adverse Events

Treatment-emergent AEs (TEAEs) will be tabulated by primary System Organ Class (SOC), High Level Term (HLT), and Preferred Term (PT). A TEAE is defined as any AE that occurs after administration of the first dose of study drug and up through 30 days after the last dose of study medication. AEs will be tabulated according to the most recent version (Version 8.1 or higher) of the Medical Dictionary for Regulatory Activities (MedDRA) by SOC, HLT, and PT and will include the following categories:

- TEAEs
- Study drug-related TEAEs
- Grade 3 or higher TEAEs
- Grade 3 or higher drug-related TEAEs
- TEAEs resulting in study drug discontinuation
- Serious AEs (SAEs), including study drug-related SAEs
- AEs of peripheral neuropathy identified by the broad search MedDRA SMQ "Peripheral neuropathy"

Additional analyses of peripheral neuropathy may also be presented.

The most commonly reported TEAEs (i.e., those events reported by $\geq 10\%$ of all patients) will be tabulated by HLT and PT.

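### The graded shift tables omit glucose and lipids, and the most-common TEAE table applies its 10% cut-off to both arms pooled

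*SAP*

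**What the plan says.** **Laboratory displays.** SAP 5.11.2 lists glucose, the lipid panel and hemoglobin A1C among the parameters to be analyzed. Actual values for hematology and serum chemistry ("including lipid panel and thyroid panel) will be summarized at baseline and over time by treatment group") are planned, together with change from baseline. The shift tables from baseline to worst post-baseline CTCAE grade are narrower. They cover five hematology parameters (hemoglobin, platelets, neutrophils, lymphocytes, leukocytes) and "Clinical chemistries: bilirubin (total), alkaline phosphatase (ALP), aspartate aminotransferase (AST), alanine aminotransferase (ALT), amylase, and lipase".

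Protocol 8.1.9 states the plan without a list: "Shift tables for laboratory parameters will be generated based on changes in NCI CTCAE grade from the baseline assessment to the worst postbaseline value". SAP Section 6, on changes from the protocol, says that none apply.

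**Named risks.** Protocol 1.3, repeated in 1.5, gives the five parameters with the most new or worsening shifts to Grade 3 or higher in the phase 2 brentuximab vedotin studies: neutrophils 11%, lymphocytes 11%, platelets 6%, leukocytes 5% and high glucose 6%. For the comparator, protocol 6.2.2 says "Hypertriglyceridemia of all grades has been recorded in 79% of patients who took bexarotene" in an early-stage study. It gives 82% for hyperlipidemia in an advanced-stage study, and 48% and 30% for hypercholesterolemia in the two studies.

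**Adverse event displays.** SAP 5.11.1.1 says: "The most commonly reported TEAEs (i.e., those events reported by $\geq 10\%$ of all patients) will be tabulated by HLT and PT". Protocol 8.1.9 uses the same pooled rule. The same SAP section also tabulates all TEAEs, drug-related TEAEs, Grade 3 or higher TEAEs and SAEs by SOC, HLT and PT with no frequency cut-off.

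**The concern.** The two arms differ in kind of toxicity, so safety displays should show what happens within each arm. Two features of the SAP work against this.

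First, the shift table is the one planned display that counts patients by worst laboratory grade from measured values alone. Glucose and lipids are not in it. The choice is also uneven: amylase and lipase are graded, while exclusion criterion 17 names uncontrolled hyperlipidemia, uncontrolled diabetes and triglyceride-raising drugs as pancreatitis risk factors. The adverse event tables are not a full substitute. Under protocol 10.1.2 an abnormal value is an AE only if it leads to action or the investigator judges it clinically significant, and SAP 5.3 confirms that investigators know the treatment.

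Second, a cut-off on the pooled total dilutes an event that occurs mainly in one arm. The condensed table then favors events common to both arms.

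**Working it through.** **1. Glucose and lipids against the shift-table list**

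- Neutrophils, lymphocytes, platelets, leukocytes: named in protocol 1.3 and graded in SAP 5.11.2.
- High glucose: named in protocol 1.3, not graded. It is the only one of the five missing.
- Triglycerides and cholesterol: named in protocol 6.2.2, not graded.

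Expected Grade 3 or higher glucose shifts, if the phase 2 rate carries over: 62 × 0.06 = 3.7, about 4 patients in the brentuximab vedotin arm.

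**2. The denominator of the cut-off**

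The plan's total of 124 reproduces. With rates 0.70 and 0.40, two-sided alpha 0.05 and 90% power, the two-proportion formula without continuity correction gives 56 per arm. Adding 10% gives 56 × 1.10 = 61.6, so 62 per arm and 124 in total. (Dividing by 0.90 gives 62.2, so 63 per arm and 126 in total.)

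**3. Pooled rule**

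- Smallest qualifying count: 0.10 × 124 = 12.4, so 13 patients (13/124 = 10.5%).
- Largest count left out: 12 (12/124 = 9.7%).
- If all 12 are in one arm: 12/62 = 19.4% against 0/62.
- If the other arm has 3 events: 12 − 3 = 9, and 9/62 = 14.5%.

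The safety population counts only dosed patients, so N may differ from 124. Assuming equal arms and an even N from 100 to 130, the worst case runs from 18.0% (N = 100: 10 needed, 9/50) to 19.7% (N = 122: 13 needed, 12/61).

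**4. Either-arm rule**

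- Smallest qualifying count: 0.10 × 62 = 6.2, so 7 patients (7/62 = 11.3%).
- Largest one-arm count left out: 6/62 = 9.7%.

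Binomial probability that an event is left out of the condensed table, 62 per arm, for assumed true rates:

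| True rates (one arm / other arm) | Pooled rule | Either-arm rule |
|---|---|---|
| 15% / 0% | 0.871 | 0.159 |
| 15% / 5% | 0.527 | 0.154 |
| 20% / 0% | 0.525 | 0.024 |

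**5. Does the cut-off explain the metabolic gap?**

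The documents give no methotrexate/bexarotene split, so 31 bexarotene patients is an assumption.

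- Hypertriglyceridemia reported as an AE: 31 × 0.79 = 24.5, well above 13. It qualifies with about 17 bexarotene patients (17 × 0.79 = 13.4).
- Grade 3 or higher glucose: about 4 patients, below 13 under the pooled rule and below 7 under the either-arm rule.

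The two points are therefore separate. Changing the cut-off would not bring Grade 3 or higher glucose into view; only the graded laboratory table would.

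**The case against.** The strongest reply is that little is lost.

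- **Full TEAE tables exist.** An event below the 10% line still appears in the uncut tables, and Grade 3 or higher TEAEs have their own. This stands. A reader might infer that such events drop out of the safety report; the SAP does not support that.
- **Laboratory toxicity can reach the AE tables.** Protocol 10.2 treats clinically relevant laboratory deterioration as an AE, and every AE is CTCAE-graded. Section 6.2.2 ties lipid-lowering and thyroxine doses to laboratory results, so many bexarotene abnormalities would count through therapeutic intervention. This also stands, so it would be wrong to say that no graded view of metabolic toxicity is produced. The remaining gap is a count that does not pass through investigator judgement.
- **By-visit summaries include minimum and maximum (SAP Section 5).** True, but an extreme value does not say how many patients reached each grade.
- **The protocol leaves details to the SAP.** Section 8.1 says so, and 8.1.9 does not promise a table for every parameter. Protocol 7.4.15 lists the lipid panel apart from serum chemistry, so a promise of lipid shift tables is arguable, although SAP 5.11.2 itself places lipids within serum chemistry. Glucose is in the protocol's serum chemistry list. A reader might call this a breach of protocol; the documents support only an unexplained narrowing. The pooled cut-off is in both documents and is no deviation.
- **The 19.4% is a worst case.** It needs zero events in the other arm, as the working shows.

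A reader might also infer that the pooled cut-off hides the main metabolic risks. Step 5 shows otherwise for hypertriglyceridemia. Hypothyroidism (29% to 40% in protocol 6.2.2) could fall either side of the line: 31 × 0.29 = 9.0 and 31 × 0.40 = 12.4 miss 13, but 33 × 0.40 = 13.2 reaches it. That turns on a split the documents do not give.

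**Conclusion.** The point holds as a minor one about safety displays. No efficacy estimate or test is affected.

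Of the five parameters the protocol singles out for Grade 3 or higher shifts, glucose alone has no graded laboratory table. The same is true of triglycerides and cholesterol. The expected number of glucose shifts is small, about 4 of 62, assuming the phase 2 rate in other lymphomas applies here. At that frequency a patient count by grade is more informative than a mean over time.

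The pooled cut-off can leave an event in up to 12/62 (19.4%) of one arm out of the most-common TEAE table, and out of that table only. This assumes 62 dosed patients per arm and no events in the other arm.

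The documents make no comparable case for creatinine, which is also off the list: protocol Table 6-2 places raised creatinine among the rare methotrexate toxicities (under 1%).

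**What to change.** In SAP 5.11.2, add glucose, triglycerides and cholesterol to the CTCAE shift tables. If the short list is intended, record it with reasons in SAP Section 6 instead.

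In SAP 5.11.1.1 and protocol 8.1.9, define the most commonly reported TEAEs as those occurring in at least 10% of patients in either treatment arm.

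The cost is a few extra rows in tables already planned. Glucose and the lipid panel are already collected under the Schedule of Events, so no new visit, sample or data field is needed.
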